3. STUDY DESIGN

The study is a phase III, stratified, randomized, observer-blind, non-influenza comparator-controlled, multicenter study to evaluate the efficacy, safety and immunogenicity of an MF59-adjuvanted quadrivalent subunit influenza vaccine compared with a non-influenza comparator vaccine in subjects ≥ 65 years of age.

The study vaccine, aQIV, contains 15 μg of each of the four seasonal influenza strains (A/H1N1, A/H3N2, B [Yamagata and Victoria lineages]) and MF59 adjuvant. The non-influenza comparator (Boostrix[®]) vaccine will be used to provide a comparative assessment for efficacy, immunogenicity and safety.

Approximately 10,692 subjects ≥ 65 years, 5,346 per vaccine group will be randomized to receive either aQIV or non-influenza comparator in a 1:1 allocation ratio, stratifying according to age (≥ 65 to 74 and ≥ 75 years), study site and comorbidity status (at risk/not at risk). Each subject will have two periods of study participation: Treatment Period (Day 1 to Day 22) and Follow-up Period (Day 23 to Day 366). The final study size is based on the number of laboratory confirmed cases of influenza, so that the ultimate number of subjects enrolled will be determined by the actual attack rates of influenza during the conduct of the study. If the number of influenza cases range between 119 and 238, unblinded interim analyses for efficacy and futility will be performed by an independent Data Monitoring Committee (DMC). Once the number of RT-PCR confirmed influenza cases is ≥ 238 the trial will be stopped and unblinded, and the final analysis will be performed. Stopping rules for futility and efficacy and any additional details regarding the DMC can be found in the DMC Charter.

The study procedures consist of four (4) clinic visits (on Days 1, 22, 181 and 366), and three (3) safety phone calls on Days 15, 91, and 271. Subjects participating in the solicited safety subset will receive an additional diary card reminder phone call on day 3.

Additionally, all subjects will receive, at a minimum, weekly phone calls or messages to assess for primary protocol-defined ILI symptoms during the first active ILI surveillance period, defined as from Day 1 through Day 181 or until the end of the regional seasonal influenza season, whichever is longer. The purpose of the ILI surveillance phone calls/message is to trigger a clinic or home visit to collect a nasopharyngeal swab.

Subjects will also be asked for the duration of the trial (through day 366) to contact the site at the onset of ILI symptoms to schedule a clinic visit for NP swab collection.

After an initial screening, subjects will be vaccinated with a single dose of aQIV or non-influenza comparator on Day 1. Subjects will be observed for at least 30 minutes post-vaccination on Day 1 for any immediate reactions. All subjects will receive a Subject Diary along with instructions to ensure proper completion and assessment on reactogenicity.

During the remaining follow-up period of the study, safety data including adverse events leading to withdrawal, AESI, NOCD and SAE and concomitant medication use related to these events will be captured via safety phone calls or clinic visits throughout the remainder of the trial (up to Day 366).

For further details please refer to section 3.0 of the protocol.

Table 3-1: Time and Events Table – Treatment Period

		Visit Type	Clinic Visit	Reminder Phone Call ^b	Safety Phone Call	Clinic Visit
		Study Day	1	3	15	22
		Visit Window (Days)	N/A	+/- 1	+/- 3	-1 to +4
		Visit Number	1		2	3
Study Event	References in the protocol					
Study Treatment						
Vaccination	Section 5.2	X				
Screening and Safety						
Informed Consent ^a	Section 5.1.1	X ^f				
Medical History	Sections 5.1.2	X ^f				
Physical Exam	Sections 5.1.2 and 5.3.1	X ^{c, f}			X	
Exclusion/Inclusion Criteria	Section 4.0	X ^f				
Randomization	Section 5.1.4	X ^f				
30 Minutes Post Injection Assessment	Section 5.2.1	X				
Subject Diary Dispensed with Training ^b	Section 5.2.1	X				
Subject Diary Reminder Call ^b	Section 5.2.2		X			
Subject Diary Reviewed and Collected ^b	Section 5.3.1				X	
Assess all AEs	Sections 7.1.1 and 7.1.3	X		X	X	
Assess SAEs	Section 7.1.4	X		X	X	

75

	Visit Type Study Day Visit Window (Days) Visit Number	Clinic Visit	Reminder Phone Call ^b	Safety Phone Call	Clinic Visit
		1	3	15	22
		N/A	+/- 1	+/- 3	-1 to +4
		1		2	3
Study Event	References in the protocol				
Assess for NOCDs, AEs leading to withdrawal, ILI and AESIs	Sections 7.1.4.1 and 7.1.3	X		X	X
Assess Relevant Medications/ Vaccinations	Sections 5.1.2 and 6.5	X		X	X
Efficacy					
ILI Instruction Sheet Dispensed	Section 5.2.1	X			
ILI Booklet Dispensed with Instructions	Section 5.2.1	X			
Message/ Phone Call to Assess ILI	Section 5.3.3	X ^d			
Immunogenicity					
Serology Blood Draw ^e	Section 3.5	X ^f			X

4. RANDOMIZATION AND BLINDING

4.1 Method of Group Assignment and Randomization

Approximately 10,620 subjects ≥ 65 years will be randomized to receive either aQIV or non-influenza comparator in a 1:1 allocation ratio, stratifying according to age (≥ 65 to 74 and ≥ 75 years), study site and comorbidity status (at risk/not at risk). Each randomized subject will be automatically assigned a unique Subject identification (ID) and Pack ID indicating the assigned treatment. The Subject ID will be the subject's unique identification number for all CRFs and associated study documentation that will be used for duration of the study.

The Subject ID consists of a 7-digit number resulting from the combination of the site number, and the subject's order of randomization at the site. After randomization, the Screening Number ceases to be used and remains in the Screening and Enrolment Log only. The list of randomization assignments is produced by the Interactive Response Technology (IRT) service provider and approved by Seqirus or delegate.

One season in which at least 2800 subjects are anticipated to be enrolled will be selected for the collection of immunogenicity samples. Samples from first 2800 subjects participating in the selected season (1,400 from each treatment arm) will be collected at Day 1 (baseline) and Day 22 (Visit 3). In order to maintain the study blind equal numbers of subjects from both treatment groups will be asked to provide blood specimens. After all of the specimens have been obtained, a subset of subjects with both samples collected will be randomly selected on a 4:1 ratio (1,362 aQIV; 340 Boostrix) for the purpose of completing the analysis of the immunogenicity objectives. The selected subjects will constitute the Immunogenicity Set. The samples from the selected subjects will be randomized into batches for HI testing in such a way that both samples from one subject are contained within one batch, but the sequence of samples is random. See [section 4.2](#) for discussion of maintaining the study blind with respect to the selected Immunogenicity Set subjects. Serum samples from subjects with RT-PCR confirmed influenza, along with a subset of subjects who did not have RT-PCR confirmed influenza, may be tested to estimate the correlate of protection. The serologic component of the correlate of protection will be measured using either a validated haemagglutination inhibition (HI) and/or other immunological assays (such as microneutralization).

Twenty percent of subjects (every 5th subject enrolled from each treatment arm) will be designated during randomization, across all sites and countries, for Solicited Safety Set, see [section 7.5](#).

For further details please refer to Section 5.1.4 of the protocol.

4.1.1 Definition of Randomization/Vaccination Errors

The list below provides some examples of potential errors that may occur during vaccination:

- Subject was vaccinated with a vaccine different from the one assigned at randomization
- Subject was vaccinated with the correct vaccine but received a lower volume than planned
- Subject randomized in the wrong stratum.

Differentiation between incorrect stratification and mis-dosing:

A mis-dosing is defined as when a subject receives a vaccine other than the one assigned by randomization. Mis-dosing is a Clinical Study Report (CSR)-reportable Protocol Deviation (PD) and should be analyzed as randomized in Full Analysis Set (FAS), excluded from Per Protocol Set (PPS), analyzed as treated for Safety.

Incorrect stratification is defined as enrollment and randomization of a subject based on incorrect stratification information at baseline. Incorrect stratifications should be classified as major or minor stratification errors.

- Major stratification errors: resulting in administration of incorrect dosage or schedule, not corrected on time, i.e. not corrected before administration of the vaccine. These will be handled as CSR-reportable PD.
- Minor stratification errors: not having impact on dose/schedule administered. These will *not* be considered as CSR reportable PD.

Stratification error	FAS	PPS	Safety Set
Minor	Analyze as corrected	Analyze as corrected	Analyze as corrected
Major	Analyze as originally stratified	Exclude from analysis	Analyze as corrected

Please see [section 7](#) of this document for a complete guidance on how vaccination errors are handled in the statistical analysis.

4.1.2 Forced Randomization

Forced randomization will not be utilized in this trial.

4.2 Blinding and Unblinding

Selection of the subject for inclusion in Immunogenicity Set (1,362 from aQIV; 340 from Boostrix arm) among approximately 2,800 subjects for which blood samples will be collected will be performed by the unblinded study statistician. The handling of all samples selected will be performed by unblinded team members. The list of subjects selected for the Immunogenicity Set will be considered as unblinded information and thus kept in the unblinded study area until the database is locked and study is officially unblinded.

Unblinded teams will be used for preparation of the reports for the DMC and the interim analysis, see [sections 14](#) and [15](#). For details please refer to section 3.3 of the protocol.

If a subject is unblinded during the study, it is to be documented as a as CSR-reportable PD, except for subjects unblinded by Pharmacovigilance due to suspected unexpected serious adverse reactions (SUSAR). The unblinding will be documented appropriately.

The unblinded subject(s) are excluded from the PPS. Unblinded subjects will be included in the FAS and safety sets.

5. SAMPLE SIZE AND POWER CONSIDERATIONS

Efficacy objectives:

Sample size and power consideration for the aQIV efficacy objective is based on criteria for demonstrating efficacy in placebo controlled studies provided in CBER guidance, specifically that the study should be powered to assess the lower bound of the two-sided 95% CI of vaccine effectiveness, anticipated to be substantially above zero. This study is planned using a group sequential design. The power of Cox Regression which is planned to be used for analysis is dependent on the overall number of influenza cases, so the sample sizes on number of subjects described in this section is provided more for operational reasons. Additional information on the planning of number of subjects that may need to be enrolled if it is decided to continue enrolment after interim analyses is described in [Section 8.6](#).

For the primary efficacy objective: with 1-sided alpha of 2.5% and assuming an attack rate of influenza of 3.5% among subjects enrolled in the non-influenza comparator group and 1.4% among the aQIV group, i.e. 60% assumed vaccine efficacy for aQIV, 238 events (i.e. 4,860 subjects per group under the assumed ERs) are needed with 86.5% power to show the absolute efficacy of aQIV versus non-influenza comparator, in preventing first occurrence RT-PCR-confirmed influenza A and/or B, due to any strain of influenza regardless of antigenic match to the strains in aQIV, in subjects ≥ 65 years of age, using a margin of 40% for lower bound of the CI for absolute vaccine efficacy.

For the first secondary efficacy objective: with a group vaccine efficacy of 65% but expecting conservatively reduced event rates of influenza cases due to matched strains of 2.5% among subjects in the non-influenza comparator group and 0.9% among the aQIV group then 144 events has estimated power approximately 88.5% to show the absolute efficacy of aQIV versus non-influenza comparator, using a margin of 40% for lower bound of the CI.

Assuming a drop-out rate of 10%, approximately 10,692 subjects ≥ 65 years, 5,346 per vaccine group will be randomized to receive either aQIV or non-influenza comparator (Boostrix®) in a 1:1 allocation ratio, stratifying by age (≥ 65 to 74 and ≥ 75 years of age), study site and by low vs high risk of influenza complications (score < 50 vs ≥ 50).

Immunogenicity objective:

Anti-HA antibody will be measured using a validated haemagglutination inhibition (HI) assay with egg-derived HA antigens from homologous strains of the virus.

The immunogenicity objective is considered as secondary and so no alpha adjustment for multiplicity will be done for the analysis therefore a significance level of 5% (2-sided) or 2.5% (1-sided) was used for sample size calculation. One season in which at least 2800 subjects are anticipated to be enrolled will be selected for the collection of immunogenicity samples. Samples from approximately 2800 subjects participating in the immunogenicity season will be obtained. In order to maintain the study blind blood samples from an equal number of subjects participating in both treatment groups will be collected at Day 1 (baseline) and Day 22 (visit 3).

After all of the specimens have been obtained a subset of samples from those collected will be randomly selected on a 4:1 ratio for analysis. In total approximately 1,702 samples are planned to be included the analysis (1,362 aQIV; 340 Boostrix). The details and the guidelines regarding the selection process of these samples can be found in the SAP.

Following assumptions from the V70_27 study in elderly adult subjects were used: specifically after aTIV vaccination, seroconversion rates, H1N1: 77%, H3N2: 74% and B: 47%, and percentages of subjects with a HI titer ≥ 40 , H1N1: 91%, H3N2: 99%, B: 64%.

With samples from at least 1,362 enrolled subjects (1,226 evaluable subjects assuming a rate of 10% for missing data in the aQIV group) there will be enough power to evaluate achievement of CBER criteria with all four strains contained in the vaccine (see [Table 5-1](#)).

Table 5-1: Power to assess CBER criteria for subjects ≥ 65 years of age

Strain	π_i (proportion in aQIV, based on data of V70_27)	π_0 (CBER threshold)	Sample size for aQIV	Marginal Power
Proportion of subjects with Seroconversion				
H1N1	77%	30%	1226	99%
H3N2	74%	30%	1226	99%
B strains	47%	30%	1226	99%
Proportion of subjects with HI titer $\geq 1:40$				
H1N1	91%	60%	1226	99%
H3N2	99%	60%	1226	99%
B strains	64%	60%	1226	82%

Safety objectives:

With 4,860 evaluable subjects in each treatment group, the probability of detecting a rare safety event which occurs at 0.001 (1/1000) rate will be 99%. With 1,000 evaluable subjects in each treatment group of the Solicited Safety Set, the probability of detecting an event which occurs at a rate of 0.002 will be $\geq 86\%$, assuming a drop-out/missing data rate of up to 5% .

Sample size calculations were performed using nQuery 7.0 and SAS 9.2.

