For the first secondary efficacy objective: With group vaccine efficacy of 65% but expecting conservatively reduced ERs of RT-PCR confirmed influenza cases due to matched strains of 2.5% among subjects in the non-influenza comparator group and 0.9% among the aQIV group then 144 events are estimated with power approximately 88.5% to show the absolute efficacy of aQIV versus non-influenza comparator, using a margin of 40% for lower bound of the 95% CI.		
Assuming a drop-out rate of 10%, approximately 10,692 subjects \geq 65 years, 5,346 per vaccine group will be randomized to receive either aQIV or non-influenza comparator (Boostrix®) in a 1:1 allocation ratio, stratifying by age groups: \geq 65 to 74 and \geq 75 years of age and by the presence or absence of medical co-morbidity (see Section 5.1.2, Screening for assessment of comorbidity and risk of complications)		

² The attack rate of 3.5% is estimated based on the attack rate published in placebo controlled studies (DeVilliers, 2009; Treanor, 2011; Frey, 2009)

Name of Sponsor: Seqirus UK Ltd.	Protocol number: V118_18	Generic name of study vaccine(s): MF59-adjuvanted Quadrivalent Subunit Inactivated Egg-derived Influenza Vaccine Tetanus Toxoid, Reduced Diphtheria Toxoid and Acellular Pertussis Vaccine, Adsorbed
--	------------------------------------	---

from influenza).

Sample Size for Secondary Immunogenicity Objective (Immunogenicity Subset):

The immunogenicity objective is considered as secondary and so no alpha adjustment for multiplicity will be done for the analysis therefore a significance level of 5% (2-sided) or 2.5% (1-sided) was used for sample size calculation.

Using the following assumptions from the V70_27 study in elderly adult subjects: specifically after aTIV vaccination, seroconversion rates, H1N1: 77%, H3N2: 74% and B: 47%, and percentages of subjects with a HI titer ≥ 40 , H1N1: 91%, H3N2: 99%, B: 64% (Table 1).

With samples analyzed from 1,362 subjects (1,226 evaluable subjects assuming a rate of 10% for missing data) in the aQIV group there will be at least 80% power to evaluate CBER criteria with all four strains contained in aQIV.

Table 1: CBER criteria for subjects ≥ 65 years of age

Strain	π_i (proportion in aQIV, based on data of V70_27)	π_0 (CBER threshold)	Sample size for aQIV	Marginal Power
Proportion of subjects with Seroconversion				
H1N1	77%	30%	1226	99%
H3N2	74%	30%	1226	99%
B strains	47%	30%	1226	99%
Proportion of subjects with HI titer ≥ 40				

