2.2 SECONDARY OBJECTIVES AND ENDPOINTS

2.2.1 Key Secondary Efficacy Objective

1. To demonstrate absolute vaccine efficacy of aQIV versus non-influenza comparator when administered as a single dose to prevent first occurrence culture-confirmed influenza, due to strains antigenically matched to the strains selected for the seasonal vaccine.

Key Secondary Efficacy Endpoints

Time to first occurrence of culture-confirmed influenza due to any strain of influenza antigenically matched from 21 days to 180 days after vaccination or at the end of influenza season whichever is longer.

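### The key secondary power of about 88.5% with 144 events is optimistic by roughly 5 to 8 points, does not match the printed event rates, and makes no stated allowance for culture yield

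*SAP*

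**What the plan says.** SAP Section 5 sizes the first secondary efficacy objective "with a group vaccine efficacy of 65% but expecting conservatively reduced event rates", with rates of "2.5% among subjects in the non-influenza comparator group and 0.9% among the aQIV group", and concludes "then 144 events has estimated power approximately 88.5% to show the absolute efficacy", "using a margin of 40% for lower bound of the CI". Protocol Section 8.5 has the same text. The one-sided 2.5% level is stated for the primary objective in the preceding paragraph, which also gives 4,860 subjects per group.

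The protocol synopsis repeats the figures but says which kind of case the rates refer to: "expecting conservatively reduced ERs of RT-PCR confirmed influenza cases due to matched strains". Protocol Section 8.5 and SAP Section 5 speak only of influenza cases due to matched strains.

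The endpoint in SAP Section 2.2.1 is "Time to first occurrence of culture-confirmed influenza due to any strain of influenza antigenically matched". Protocol Sections 3.5 and 7.2 have swabs tested by RT-PCR and also cultured, with the culture used for antigenic characterisation. Neither document states an expected culture yield. Enrolment and stopping follow the count of RT-PCR-confirmed cases (238), not of culture-confirmed matched cases.

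**The concern.** Three things do not fit together. The printed event count is not the one that the printed rates produce. The printed power looks high for 144 events when the true hazard ratio is far from 1 and the test is against a hazard ratio of 0.60. And the synopsis attaches the rates to a wider case type than the endpoint counts.

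Under the protocol (Sections 8.2.2.2 and 8.4.3.2.1) this is the only efficacy objective besides the primary with a formal success test. A reader relying on 88.5% would expect failure about 1 time in 9 under the assumed efficacy. Because the trial runs to a target of RT-PCR cases, nothing in the design secures the number of culture-confirmed matched cases.

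**Working it through.** **Inputs.** From SAP Section 5: 144 events; VE 65% (HR 0.35); margin VE 40% (HR 0.60); rates 2.5% and 0.9%; 4,860 evaluable per group; 1:1 allocation; one-sided alpha 0.025 (z = 1.96). From SAP Section 14.1, Table 1: two-stage p-value boundaries of 0.00625 (efficacy) and 0.35022 (futility) at half information, and 0.02275 at the end.

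**1. Reproducing 88.5%.** The HR relative to the margin is r = 0.35/0.60 = 0.583.
- Freedman, single look: √144 × (1 − r)/(1 + r) − 1.96 = 12 × 0.263 − 1.96 = 1.198, so power is 88.5%.
- Schoenfeld, single look: (√144/2) × |ln r| − 1.96 = 6 × 0.539 − 1.96 = 1.274, so power is 89.9%.
- Two-stage with the Table 1 boundaries and information = events/4: 88.6%. The same calculation for the primary (238 events, HR 0.40) gives 86.5%, the figure the plan prints, so this may be the source.

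All three use a variance suited to nearly equal event counts in the two arms.

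**2. Allowing for the unequal split.** With equal follow-up, HR 0.35 puts 144 × 0.35/1.35 = 37.3 events in the aQIV arm and 106.7 in the comparator arm. The standard error of the log HR is √(1/37.3 + 1/106.7) = 0.190, against √(4/144) = 0.167 with balanced events.
- Wald: 0.539/0.190 − 1.96 = 0.874, so power is 80.9%.
- Exact binomial conditional on 144 events (null share 0.6/1.6 = 0.375, true share 0.35/1.35 = 0.259): 83.7%. The exact figure moves in steps with the event count; averaged over nearby counts it is about 82%.
- Simulated Wald interval: about 83.5-83.8%.
- Wald with the primary's two-stage boundaries, futility included: 79.2%.

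**3. Events implied by the rates.** 4,860 × (0.025 + 0.009) = 165.2. The route through the primary target agrees: 238 × 3.4/4.9 = 165.1. To get 144 at these rates takes 144/0.034 = 4,235 per group, a number that appears nowhere. Using the 5,346 randomised per group widens the gap: 5,346 × 0.034 = 182. The rates give VE = 1 − 0.9/2.5 = 64%.

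Power at 165 events and HR 0.36, single look:
- Wald: split 43.7 versus 121.3, standard error 0.176, 0.511/0.176 − 1.96 = 0.935 (unrounded), so 82.5%.
- Exact conditional: 84.8%.
- Simulation with 4,860 per group: 85.1-85.7%.
- Two-stage Wald with the primary's boundaries: 80.9%.

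**4. Culture yield.** The documents give none, so these yields are assumptions, applied to 165 RT-PCR-confirmed matched cases at HR 0.36 (single-look Wald, no futility rule):

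| Assumed yield | Events | Power |
|---|---|---|
| 100% | 165 | 82.5% |
| 90% | 148 | 78.4% |
| 80% | 132 | 73.5% |
| 70% | 115 | 67.8% |
| 50% | 82 | 53.5% |

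At 80% yield the exact figure is 76.1% and simulation gives 75.9%; across methods, including two-stage, the range is roughly 72-76%. If 144 is itself the culture-confirmed count, it corresponds to a yield of 144/165 = 87%.

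**The case against.** The strongest reply is that there is no arithmetic error. Freedman's formula, applied to the stated events, VE, margin and alpha, returns 88.5%, so what remains is a choice of variance approximation. That is right, and it rules out saying that the figure cannot be obtained from its inputs. The approximation is nevertheless a poor one here: for the same 144 events the exact calculation is about 5 points lower.

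Second, 64% against 65% is rounding, since 2.5% × 0.35 = 0.875%, printed as 0.9%. That stands, and nothing rests on it.

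Third, 144 is below 165, so the mismatch does not inflate the claim; at 165 events and VE 65% Freedman gives 92%. The 144 may already contain an allowance for culture loss. That is possible, but no text says so, and the reader cannot tell which case type the 144 counts.

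Fourth, the RT-PCR wording appears only in the synopsis. That also stands: one might infer that the whole plan sizes this objective on the wrong case type, but Protocol Section 8.5 and SAP Section 5 are silent on confirmation method. The point is an unreconciled description with no stated yield.

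Fifth, the two-stage boundaries are written for the primary objective, and no futility boundary is given for the key secondary. The 79% and 81% two-stage figures are therefore illustrative, and the single-look figures are the fairer basis. Finally, study success rests on the primary efficacy objective with acceptable safety, and the key secondary is tested only after it, so the consequence is limited.

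**Conclusion.** The point holds as a matter of optimism and reconciliation. For 144 events at VE 65%, power is about 81-84% on a single look at one-sided 2.5%, against the stated 88.5%: an overstatement of about 5 to 8 points, or about 9 if the primary's two-stage boundaries are carried over. At the printed rates (165 events, VE 64%) power is about 82-86% on a single look. These figures assume proportional hazards, equal follow-up and full capture of the stated cases. If the rates are RT-PCR rates, as the synopsis says, any culture yield below 100% lowers power further; the documents do not allow the size of that loss to be fixed.

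A reader might infer that power is 81% at best, or that the risk of failure is at least 1 in 5. Neither is supported. With 165 events at VE 65% the Wald figure is 85.9% and the exact figure 88.3%. With 144 events the exact failure risk is 16.3%, about 1 in 6.

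**What to change.** Revise the paragraph in the protocol synopsis, Protocol Section 8.5 and SAP Section 5 in the same words:

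- State whether 144 counts culture-confirmed matched cases (87% of 165) or RT-PCR-confirmed matched cases, and reconcile it with the 2.5% and 0.9% rates at 4,860 per group.
- State the assumed culture yield and the culture-confirmed event count that follows from it.
- Name the power formula and use a variance that reflects the unequal event split. If 144 is the culture-confirmed count, report about 81-84% at VE 65%; otherwise report the lower figure for the stated yield.
- Say whether the power refers to a single look or to the level left after an interim analysis, since SAP Section 12.2 reduces alpha in that case. At one-sided 0.02275 the single-look Wald figure for 144 events falls from 80.9% to 79.8%.

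The cost is text in three places and a less favourable stated power. Enrolment and the 238-case target do not change.
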